3.1 Revision History

Version	Date of Revision	Revision
1.0	2019 October 24	Original SAP

4 ABBREVIATIONS AND DEFINITION OF TERMS

The following abbreviations are used within this SAP.

ABOUT	Assessment of behavioral outcomes related to tobacco and nicotine products
AE	Adverse event
ANOVA	Analysis of variance
ANCOVA	Analysis of covariance
ATC	Anatomical Therapeutic and Chemical
AUC	Area under the concentration-time curve
AUC _(0-4h)	Partial AUC, assessed between 0 and 4 hours post P3P use
BLOQ	Below the Lower limit of Quantification
BMI	Body mass index
BoExp	Biomarker of exposure
CEMA	2-cyanoethylmercapturic acid
CI	Confidence interval
C _{max}	Maximum concentration
COT	Cotinine
CRF	Case report form
CRO	Contract research organization
CTCAE	Common terminology criteria for adverse events and common toxicity criteria
CTMS	Clinical trial management system
CV	Coefficient of variation
CYP2A6	Cytochrome P450 2A6
DDE	Drug Dictionary Enhanced
ECG	Electrocardiogram
eCRF	Electronic Case Report Form
EOS	End of study
FEV ₁	Forced expiratory volume in 1 second
FVC	Forced vital capacity
HCOT	Trans-3'hydroxycotinine
HIV	Human immunodeficiency virus
HnB	Heat not Burn
HPHCs	Harmful and potentially harmful constituents
ICF	Informed consent form
ICH	International Conference on Harmonization
LLOQ	Lower limit of quantification
MedDRA	Medical dictionary for regulatory activities
PK	Pharmacokinetic(s)
PMPSA	Philip Morris Products S.A.
PT	Preferred Term
QTcB	QT Interval Corrected using Bazett's Formula

QTcF	QT Interval Corrected using Fridericia's Formula
RSR	Research Study Report
SAE	Serious adverse event
SAP	Statistical analysis plan
SD	Standard Deviation
SOC	System Organ Class
T	Time point
T ₀	Time point of start of product use
t _{max}	Time to maximum concentration
TFL	Tables, Figures, and Listings
Total NNAL	Total 4-(Methylnitrosamino)-1-(3-pyridyl)-1-butanol
ULOQ	Upper limit of quantification
VAS	Visual analogue scale
WBC	White blood cell (count)
WHO	World Health Organization
λ _z	Terminal elimination rate constant

The following special terms are used in this SAP:

Screen failure	Subject who signs the ICF but is not enrolled at Admission.
Enrollment	On Admission Visit (Day -1) for eligible subjects after all applicable inclusion and exclusion criteria have been satisfactorily assessed and met.
First product use time point	Start of the product test use.
Randomization	Allocation of the respective product, P3P-1mg or P3P-2mg, after product test on Day -1.
End of Study	The end of the study (EOS) for a subject is defined as either the Discharge at Day 30, or the date of early termination of the subject, plus the Safety Follow-Up Period.
	The end of the whole study corresponds to the individual EOS of the last subject.
Safety Follow-up	After discharge on Day 30 or early termination, a 14-day Safety Follow-Up will be done.

5 STUDY OBJECTIVES AND ENDPOINTS

5.1 Primary Objective and Endpoints

1. To assess nicotine pharmacokinetics following use of a single P3P-1mg or P3P-2mg product on Day 1 and Day 30.

Endpoints:

- Plasma nicotine time-concentration profile from prior product use to 4 hours post start of product use;
- PK parameters: maximum plasma concentration (C_{max}); time to maximum concentration (t_{max}); Area under the concentration-time curve from start of product use to 4 hours ($AUC_{(0-4h)}$).

5.2 Secondary Objectives and Endpoints

1. To evaluate the pharmacodynamic effects (subjective effects and related behavioral assessments) of the two P3P variants.

Endpoints:

- Visual Analogue Scale (VAS)-craving assessment in parallel with PK assessment on Day 1 and Day 30;
- Sensory Questionnaire on Day 1 and Day 30;
- ABOUT™-Product Experience Questionnaire on Day 1 and Day 30.

2. To assess product acceptance and puffing/inhalation behavior of both P3P variants

Endpoints:

- Product acceptance questionnaire on Day 1 and Day 30;
- Puffing/inhalation behavior question:
 - Evaluated by site staff on Day 1 and Day 30
 - Answered by subject on Day 2, Day 7, Day 15, Day 22 and Day 29.

3. To assess nicotine/tobacco product use.

Endpoints:

- Number of P3P, cigarettes, e-cigarettes or/and other nicotine/tobacco product use from Day 1 to Day 30;
- Change in the number of cigarettes used throughout the study as compared to the reported number at Screening.

4. To assess safety and tolerability during the study.

Endpoints:

- Incidence of adverse events (AEs), serious adverse events (SAEs);
- Frequency of adverse events (AEs), serious adverse events (SAEs);

- Incidence of P3P product events including malfunction/misuse;
- Frequency of P3P product events including malfunction/misuse;
- Physical examination changes from baseline;
- Cough assessment changes from baseline (VAS and three Likert scales);
- Electrocardiogram (ECG) changes from baseline (heart rate, PR, QRS, QT, QTcB, QTcF intervals);
- Vital signs changes from baseline (systolic and diastolic blood pressure, pulse rate and respiratory rate);
- Spirometry changes from baseline (FEV1, FEV1 % predicted, FVC, FVC % predicted, FEF 25, FEF 25 % predicted, FEF 75, FEF75 % predicted, FEF 25-75, FEF 25-75 % predicted, FEV1/FVC);
- Changes from baseline in clinical chemistry, hematology, and urinalysis safety panel;
- Concomitant medications.

5. To assess the exposure to harmful and potentially harmful constituents (PHHCs) in spot urine expressed as concentration adjusted for creatinine from Day -1 to Day 30.

Endpoints:

- Biomarker of exposure (BoExp) to nicotine: Nicotine equivalents (NEQ);
- BoExp to NNK: 4-(Methylnitrosamino)-1-(3-pyridyl)-1-butanol (total NNAL);
- BoExp to Acrylonitrile: 2-cyanoethylmercapturic acid (CEMA).

6. To assess tobacco and nicotine containing product dependence at Day -1 and at Day 30.

Endpoint:

- ABOUTTM-Dependence Questionnaire.

7. To assess cytochrome P450 2A6 (CYP2A6) enzymatic activity at Day 1 and at Day 30.

Endpoint:

- Molar metabolic ratio of trans-3'-hydroxycotinine/cotinine in plasma.

8. To estimate the amount of powder extracted from P3P used for PK assessment.

Endpoint:

- Weight difference of P3P before and after use.

5.3 Study Hypotheses And Evaluation Criteria

5.3.1 Hypotheses

The study will be descriptive in nature. However, for the ANOVA tests, the following hypothesis will be tested:

$$H_0: \mu_1 = \mu_2$$

$$H_1: \mu_1 \neq \mu_2$$

where μ_1 and μ_2 are the means (arithmetic or geometric) for each product variant, respectively.

6 INVESTIGATIONAL PLAN

6.1 Study Design

This is a randomized, double-blinded, 2-arm parallel groups, single-center study conducted in current adult smokers willing to switch from smoking cigarettes to using P3P for 1 month. Subjects were asked to use no more than 15 P3P products per day over 1 month and the study will include 2 occasions of confinement period (3 days at V2 and 2 days at V6). From the start of the exposure period onwards, subjects will be instructed to use P3P exclusively. Subjects will be randomized to use either P3P-2mg or P3P-1mg.

1) Screening and Admission (from the ICF Signature [V1] to Randomization at V2 [Day -1]):

A Screening Visit will be conducted within 3 weeks prior to Admission to the investigational site. A demonstration of P3P, without product use, will be done by the investigational site staff during the Screening Visit.

Subjects will return to the investigational site for Admission (Day -1). Subjects should have been fasting for at least 6 hours prior to Admission. After confirmation of eligibility, subjects will be enrolled. All subjects that are not enrolled will be considered as screen failures. At Admission, enrolled subjects will perform a product test using up to 6 P3P products (alternating between P3P-1mg and P3P-2mg). In order to continue in the study, each subject will need to test at least one product of each P3P variant during the product test. Subjects should be abstinent from the use of any tobacco/nicotine containing products for at least 4 hours prior to product test. After the product test, subjects not willing and/or not ready to use P3P will be discontinued from the study. Subjects willing and ready to use P3P during the study will be randomized either to P3P-1mg or P3P-2mg in a 1:1 ratio and will start their first overnight (confinement) period for pharmacokinetics assessments on Day 1. The subjects and the Investigator will be blinded to the randomization arm.

2) The Exposure Period (from V2 [Day 1] to Discharge at V6 [Day 30]):

On Day 1, after at least 10 hour abstinence from any tobacco/nicotine containing products, subjects will use a single P3P product, as randomized, for a duration of up to 15 minutes. The start of product use will be defined as T_0 .

A total of 11 blood samples will be taken for PK parameter estimation. Three blood samples will be taken prior to the product use (T_0) and 8 additional blood samples will be taken at specific timepoints within 4h after the start of product use.

Pharmacodynamic effects related to craving will be assessed using a VAS scale at different time points before, during and after product use. Product evaluation using the ABOUTTM-product experience questionnaire, the sensory questionnaire and the product acceptance questionnaire will be assessed after the end of product use.

Each P3P used for PK assessment will be weighted before and after product use to estimate the amount of nicotine delivered in the aerosol.

After the end of blood sampling for PK estimation, subjects will stay on-site until the evening of Day 2 and will be allowed to use up to 15 P3P products/daily during these two days. Safety assessments will be performed both on Day 1 and Day 2.

Subjects will be instructed to use exclusively P3P for the entire 1-month duration of the exposure period (from the end of V2 until discharge at V6). Use of cigarettes and/or other tobacco and nicotine containing products during the ambulatory exposure period will not be a reason for discontinuing a subject from the study, but should be avoided as much as possible. At V2, subjects will be trained on how to record their use of P3P and other tobacco/nicotine containing products in a designated website during the entire ambulatory exposure period.

Subjects will return to the investigational site for weekly visits V3 (Day 7), V4 (Day 15), V5 (Day 22) and V6 (Day 29) with a visit time window of \pm 2 days each. The visit days and windows will be calculated from Day 1. During these visits product will be resupplied and selected safety assessments will be performed.

At V6 subjects will remain at the investigational site for their confinement period for pharmacokinetics assessments on the second day of this visit, Day 30. There will be a washout period from any nicotine/tobacco containing products of at least 10 hours before T_0 to allow adequate background correction of the plasma nicotine concentrations. The assessments performed at Day 30 will be the same as those described for Day 1.

3) The Safety Follow-Up Period (from Discharge or Early Termination plus 14 days)

After discharge on Day 30 or early termination, subjects will enter a 14-day Safety Follow-Up Period during which new AE/SAEs will be collected and ongoing AEs/SAEs will be

followed-up by the site. At the end of the Safety Follow-Up all subjects will be contacted via phone in order to check the status of the ongoing AEs and also to collect any new AEs experienced by the subjects. Subjects should be contacted 14-days after Day 30. In case they cannot be reached two additional attempts at the next 2 consecutive days will be made. If the subjects cannot be reached after the three attempts they will be declared lost to follow-up. Phone calls should be recorded in the source documents. Any non-serious AE that is ongoing at the time of discharge or early discontinuation or previously reported during the Safety Follow-Up will be followed-up by the Investigator or designee during Safety Follow-Up Period until it has been resolved, stabilized (i.e., no worsening of the condition), or an acceptable explanation has been found (e.g., a chronic condition) or the subject is lost to follow up. At the end of the Safety Follow-Up Period, all ongoing non-serious AEs will be documented as "ongoing" and no further follow-up information will be sought for them by the Investigator or designee. At that point, the Investigator will assess whether the subject should be referred to his/her General Practitioner to have their ongoing AEs addressed accordingly. All SAEs will be followed up by the Investigator until resolution, stabilization or the determination of a plausible explanation for them was found, regardless of the end of the Safety Follow-Up Period.

6.2 Selection of Study Population

Sixty female or male healthy adult subjects who have smoked between 5 and 15 cigarettes per day for the last 3 months prior to Screening will be randomized in this study. Each randomization group (P3P-1mg, P3P-2mg) will be stratified on sex distribution to ensure that at least 40% of each sex is randomized in each exposure group.

6.2.1 Inclusion Criteria

Subjects must meet all of the following inclusion criteria to be enrolled into the study:

Inclusion Criteria	Rationale	Screening	Admission (Day -1)
1. Subject has signed and dated the ICF and is able to understand the information provided in it.	Administrative	X	
2. Subject is male or female aged between 21 and 65 years old inclusive.	Safety	X	
3. Subject has been a smoker for at least the last 3 years prior to the Screening visit and has smoked 5 to 15 commercially available cigarettes per day over the last 3 months prior to Screening.	Effect	X	
4. Subject has a positive urinary cotinine test (cotinine \geq 200 ng/mL).	Effect	X	X

5. Subject does not plan to quit smoking in the next 2 months.	Safety	X	X
6. Smoking, healthy subject as judged by the Investigator or designee based on available assessments from the Screening period (e.g., safety laboratory, spirometry, vital signs, physical examination, chest X-ray, ECG and medical history).	Safety	X	
7. Availability for the entire study period and willingness to comply with study procedures, including intermittent dietary restrictions.	Effect	X	X
8. Ready to switch from smoking cigarettes to using P3P for the duration of the study.	Effect	X	

6.2.2 Exclusion Criteria

Subjects who meet any of the following exclusion criteria must not be enrolled into the study:

Exclusion Criteria	Rationale	Screening	Admission (Day -1)
1. As per the Investigator's judgment, the subject cannot participate in the study for any reason other than medical (e.g., psychological, social reason).	Safety	X	
2. Subject is legally incompetent, or physically or mentally incapable of giving consent (e.g., emergency situation, under guardianship, prisoners, or subjects who are involuntarily incarcerated).	Administrative	X	
3. Subject has a clinically relevant disease which requires medication (including but not limited to gastrointestinal, renal, hepatic, neurological, hematological, endocrine, oncological, urological, immunological, pulmonary, and cardiovascular disease) or any other medical condition (including safety laboratory as per CTCAE), which as per the judgment of the Investigator would jeopardize the safety of the subject.	Safety	X	

Exclusion Criteria	Rationale	Screening	Admission (Day -1)
4. As per the Investigator's judgment, the subject has medical conditions which require or will require in the course of the study, a medical intervention (e.g., start of treatment, surgery, hospitalization) which may interfere with the study participation and/or study results.	Effect	X	
5. Subject has asthma condition (post-bronchodilator $FEV_1/FVC < 0.75$ and reversibility in $FEV_1 \geq 12\%$ and > 200 mL from pre- to post-bronchodilator values).	Safety	X	
6. Subject has $(FEV_1/FVC) < 0.7$ and $FEV_1 < 80\%$ predicted value at post-bronchodilator spirometry.	Safety	X	
7. Subject has a history of hypersensitivity to [REDACTED] or menthol.	Safety	X	
8. Subject has a contraindication for using salbutamol and/or albuterol as per the summary of product characteristics for the given product	Safety	X	
9. Subject has donated or received whole blood or blood products within 3 months prior to Screening Visit.	Safety	X	
10. $BMI < 18.5 \text{ kg/m}^2$ or $\geq 32.0 \text{ kg/m}^2$.	Safety	X	
11. Subject has received medication within 14 days or within 5 half-lives of the drug prior to Admission (whichever is longer) which has an impact on CYP2A6 activity.	Effect		X
12. Subject has a positive serology test for HIV 1/2, Hepatitis B, or Hepatitis C.	Safety	X	
13. The subject has a positive alcohol breath test and/or had a history of alcohol disorder within the past 2 years.	Administrative	X	X
14. The subject has a positive urine drug test.	Administrative	X	X
15. Subject or one of their family members ^a is a current or former employee of the tobacco industry.	Administrative	X	

Exclusion Criteria	Rationale	Screening	Admission (Day -1)
16. Subject or one of their family members ^a is employee of the investigational site or of any other parties involved in the study.	Administrative	X	
17. The Subject has participated in another clinical study within 3 months prior to the Screening Visit.	Safety	X	
18. Subject has been previously screened or enrolled in this study.	Administrative	X	
19. Subject is pregnant (does not have negative pregnancy tests at Screening Visit and at Admission) or is breastfeeding.	Safety	X	X
20. For women of childbearing potential only ^b : subject does not agree to use an acceptable method of effective contraception. ^c	Safety	X	

- a. As defined by FDA guidance on Human Subject Protection (21 CFR 50.3(l), (m), 50.24(a)(6), (a)(7)(v), b)): "Family member" means among other things "parent", "spouse", "brothers, sisters, and spouses of brothers and sisters" and "any individual related by affinity...whose close association with the subject is equivalent of a family relationship"
- b. Women who are not of childbearing potential meet at least one of the following criteria:
Have undergone hysterectomy or bilateral tubal ligation,
Have primary ovarian insufficiency, or
Are medically confirmed to be post-menopausal (cessation of regular menses for at least 12 consecutive months with no alternative pathological or physiological cause).
- c. Intrauterine device, intrauterine system, barrier methods of contraception (condoms, occlusive caps) with spermicidal foam/gel/film/suppository, hormonal contraception, vasectomized partner(s), or true abstinence (periodic abstinence and withdrawal are not effective methods) from Screening until the end of the Safety Follow-Up Period.

6.3 Product Allocation and Blinding

6.3.1 Methods of Assigning Subjects to Product Variant

At Day -1, after product test, subjects who confirmed their willingness to continue in the study will be randomized using an interactive web response system (IWRS). Subjects will be randomized to one of the two arms: P3P-1mg or P3P-2mg in a 1:1 ratio.

Each randomization group (P3P-1mg, P3P-2mg) will be stratified on sex distribution to ensure that at least 40% of each sex is randomized in each group.

6.3.2 Blinding

This is a double-blind study. Neither the site staff (except designated unblinded site staff if applicable) nor the subject will be informed about the product variant the subjects have been randomized to. PMPSA and CRO personnel will not be blinded to the randomization arm. Blinding process will be described in more details in the IP handling manual.

7 DERIVED AND COMPUTED VARIABLES

Each individual change from baseline will be calculated by subtracting the individual subject's baseline value from the value at the timepoint.

Baseline definition by endpoint can be found in the different sections defining the derivation of each endpoint below and in section 12.1.4.

The geometric coefficient of variation (CV) for descriptive statistics will be calculated using the following formula:

$$CV = 100\sqrt{e^{\text{var}} - 1}$$

where var = the variance from the log transformed data.

7.1 Pharmacokinetic Parameters

For the calculation of PK parameters, the actual blood sampling times (collected in the CRF) rather than the nominal timepoints will be used in all calculations with the exception of the last collected sample prior to product use which can be considered as the T_0 value. Partial dates/times for PK assessments or T_0 will not in general be imputed.

For nicotine concentrations below the lower limit of quantification (BLOQ) :

- BLOQ values before T_0 will be imputed by LLOQ/2.
- BLOQ values after the last quantifiable value are not included in the analysis (e.g., for the calculation of AUC).
- Any BLOQ value (after T_0 and before the last quantifiable value) would need to be queried and, if confirmed, it will be imputed by LLOQ/2.

To minimize the carry-over effect in the plasma nicotine PK parameters due to limited washout periods, background-concentration correction will be applied to the nicotine concentration data.

Baseline nicotine concentration (C_0) will be defined as the last measured concentration prior to T_0 at Day 1 and at Day 30 (Visit 2 and Visit 6). The baseline correction will be implemented by calculating the PK parameters using adjusted concentration values as described below:

- Calculate the slope using a linear regression on the log concentration of the 3 pre- T_0 timepoints.
- If the slope is ≤ 0 , then use the slope to determine the elimination rate constant λ_z .

- If the slope is > 0 , then use the subject's slope that is ≤ 0 from the other visit to determine λ_z . If the subject's slopes are positive for the 2 visits, baseline corrected PK parameters will not be calculated.
- Adjust each concentration value post-baseline using the following formula:

$$cC_t = C_t - C_0 * e^{-\lambda_z t}.$$

cC_t is the corrected concentration at each time point, C_t is the concentration at each time point, C_0 is the pre-use baseline nicotine concentration at the given visit, λ_z is the elimination rate constant and t is the actual time.

If C_0 is BLOQ then there will be no baseline correction of the PK parameters. In that case cC_{max} , ct_{max} and $cAUC_{(0-4h)}$ will be considered as equal to C_{max} , t_{max} and $AUC_{(0-4h)}$, respectively.

- The following PK parameters will be derived from nicotine levels adjusted for baseline:

cC_{max}	Background-corrected maximum observed plasma concentration. cC_{max} will be reported as long as there is at least one quantifiable concentration post-exposure
ct_{max}	Time to maximum concentration cC_{max}
$cAUC_{(0-4h)}$	Background-corrected area under the plasma concentration-time curve from start of product use (T_0) to 4 hour

Additional PK parameters may be determined in order to support the interpretation where appropriate.

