#### **Confidentiality Statement**

Data and information contained in this document are considered to constitute trade secrets and confidential commercial information, and the legal protections provided to such trade secrets and confidential information are hereby claimed under the provisions of applicable law. No part of this document may be publicly disclosed without the written consent of Philip Morris Products S.A.

In a previous study conducted with P3P (ClinTrials.gov: NCT03369340), the pharmacokinetic profiles of nicotine following a single use of P3P were indicative of a partial pulmonary and partial oromucosal absorption with lower plasma nicotine levels compared to published data for single cigarette smoking (23, 24). It is well established that changing a current cigarette to a novel tobacco /nicotine-containing product requires an adaptation in product use behavior as has been described for low-yield cigarettes, e-cigarettes or a novel Tobacco Heating System (10-15). The changes in product use behaviour over time (e.g. potential changes in puffing/inhalation process) may result in changes in the nicotine PK profiles in particular in the absorption phase. For this reason, nicotine PK profiles and parameters following a single product use will be assessed at the beginning of the exposure period (Day 1) and at the end of the exposure period following adaptation to product use (Day 30). Sampling timepoints for determination of nicotine concentrations were selected to ensure reliable estimation of PK parameters.

Plasma nicotine presents a biphasic profile, with a typical rapid initial disposition half-life ( $t_{1/2\alpha}$ ) of 1.35 hours, followed by a slower terminal elimination half-life ( $t_{1/2\beta}$ ) of 17 hours (28). To ensure a full nicotine washout between each product use, a separation of 3 days would have been required ( $\sim 5 \times$  elimination  $t_{1/2\beta}$ ). Based on nicotine population PK modeling, it was estimated that subjects' nicotine has entered in the terminal elimination phase with concentrations decreasing according to the terminal elimination rate constant ( $\lambda_z$ ) after 8 to 10 hours post administration. As a consequence, a minimum of 10 hours have been established in this study design before the start of product use for PK assessment to ensure appropriate washout of nicotine. Background-concentration correction will be applied to adjust for any residual carry-over effects as detailed in section 12.5.1.

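### Imputed pre-use BLOQ values can enter the λz regression in SAP 7.1, and the resulting slope can be lent to the subject's other visit

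*SAP*

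**What the plan says.** SAP 7.1 builds the background correction in steps.

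- Imputation: "BLOQ values before T_0 will be imputed by LLOQ/2". No exception is made for the slope regression.
- Slope: "Calculate the slope using a linear regression on the log concentration of the 3 pre- T_0 timepoints". No minimum number of quantifiable values is set.
- Acceptance: if the slope is zero or negative, "then use the slope to determine the elimination rate constant".
- Borrowing: if the slope is positive, "then use the subject's slope that is ≤ 0 from the other visit".
- Both slopes positive: "If the subject's slopes are positive for the 2 visits, baseline corrected PK parameters will not be calculated".
- BLOQ baseline: "If C_0 is BLOQ then there will be no baseline correction of the PK parameters".

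Protocol 12.5.1 uses the same zero-or-less criterion, and Protocol 12.1.4 the same half-LLOQ imputation. SAP 7.1.2 requires at least three concentrations above the LLOQ before an AUC is calculated; the slope has no comparable minimum. SAP 7.1.3 covers anomalous concentrations, not slopes.

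**The concern.** An imputed constant is not a measurement, yet the rules let it act as one. Three BLOQ samples become three identical numbers, and the fitted slope is zero whatever the subject's elimination rate. Zero passes the acceptance test. The visit that produced it is not corrected, because its own C0 is BLOQ, but nothing stops its slope from becoming λz for the other visit. A mixture of quantifiable and imputed values can instead give a steep decline that reflects only the step down to LLOQ/2.

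Under SAP 12.5.1, log cAUC(0-4h) is a primary analysis variable. Its Day 1 value is the ANCOVA covariate and one side of the Day 30 to Day 1 ratio; its Day 30 value is the ANCOVA response and the other side. There are about 30 subjects per arm, so a few distorted values could matter.

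**Working it through.** The documents give no figure for this point, so there is nothing to reproduce. The stated rules were applied directly.

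**Inputs from the documents.** Pre-T0 times of -1, -0.5 and -0.083 h (SAP 11.2.1); post-T0 times of 4, 7, 10, 15 and 30 min and 1, 2 and 4 h; linear trapezoid (SAP 7.1.2). Protocol 4.2 describes an initial half-life of 1.35 h "followed by a slower terminal elimination half-life" of 17 h, so the benchmark is λz = ln2/17 = 0.0408/h. Protocol 2.1.2 gives a Cmax of 1.1 ng/mL for the 1 mg variant and 2.1-3.1 ng/mL for the 2 mg variants.

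**Assumed.** The P3P profile rises linearly to Cmax at 15 min and then declines with a 1.35 h half-life. C0, LLOQ and assay error are not given and are shown as ranges.

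**1. Slopes produced by imputation.** b = Σ(t - t̄)·ln C / Σ(t - t̄)². The mean time is -0.528 h, the deviations are -0.472, 0.028 and 0.444, and the sum of squares is 0.421. With L the LLOQ:

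- L/2, L/2, L/2: b = 0 for any L. In floating point, one least-squares routine returned +2.9e-16, which a strict test for a positive slope would read as positive. The software, not the data, then decides whether a 0 is lent or the borrower's parameters go missing.
- 1.02L, L/2, L/2: b = -0.472 × ln(2.04) / 0.421 = -0.80/h, a half-life of 0.87 h.
- L, L, L/2: b = 0.444 × (-ln 2) / 0.421 = -0.73/h, a half-life of 0.95 h.

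In all three patterns the last value is BLOQ, so the visit itself is not corrected but can still lend.

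**2. Background area removed over 0-4 h.** A(λ) = (1 - e^(-4λ))/λ, in units of C0:

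| λz | Area | Change in borrower's cAUC |
|---|---|---|
| 0.0408/h (17 h) | 3.69 | reference |
| 0 (borrowed) | 4.00 | -0.31 × C0 |
| 0.73/h (borrowed) | 1.36 by trapezoid, 1.29 exact | about +2.3 to +2.4 × C0 |
| 0.80/h (borrowed) | 1.26 by trapezoid, 1.20 exact | about +2.4 to +2.5 × C0 |

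If the true pre-use decline were faster than the benchmark, a borrowed 0 would err by more: 0.62 × C0 at an 8 h half-life and 1.10 × C0 at 4 h.

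**3. Size of a borrowed 0 relative to cAUC.** The assumed profile gives AUC(0-4h) = 2.03, 3.88 and 5.72 ng·h/mL for Cmax 1.1, 2.1 and 3.1.

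- C0 = 1 ng/mL: 0.308/2.03 = 15%; 0.308/3.88 = 8%; 0.308/5.72 = 5%.
- C0 = 2 ng/mL: 30%, 16% and 11%.

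**4. cCmax.** At 15 min a borrowed 0 subtracts too much by 1 - e^(-0.0408 × 0.25) = 1.0% of C0, which is negligible. A borrowed steep slope subtracts too little by 0.990 - 0.833 = 16% to 0.990 - 0.819 = 17% of C0.

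**5. Can borrowing occur?** With a 17 h half-life the concentration falls only 3.7% in the 55 min before the last pre-use sample. The standard error of the slope is the assay error divided by √0.421 = 0.649. The chance that a fully quantifiable visit has a positive slope is then 9%, 30% or 40% at assumed assay errors of 2%, 5% or 10%. A visit in need of a lender is not unusual.

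**6. Frequency.** Take assumed median C0 of 2 ng/mL on Day 1 and 0.4 ng/mL on Day 30, with 5% assay error and a between-subject log-SD of 0.8. An all-BLOQ slope is then borrowed in about 1%, 5% and 17% of subjects at LLOQ 0.1, 0.2 and 0.5 ng/mL. At log-SD 0.3-0.5, the LLOQ 0.2 figure falls to 0.2-2%. Other plausible inputs run from near 0% to 23%. Mixed patterns were borrowed in 0.2-0.9%. None of these inputs is in the documents.

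**The case against.** The strongest case against concerns size, not mechanism.

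- **An ordinary error.** With 5% assay error and a 17 h half-life, fully quantifiable slopes that pass the zero-or-less test have a mean absolute background-area error of 0.32 × C0, and 39% of them exceed 0.31 × C0. A lent 0 is about as wrong as a typical slope the plan would keep. This stands, and it limits the gain from the fix. It does not justify treating imputed constants as an elimination rate.
- **Existing cover.** SAP 12.5.1 repeats the ANCOVA on uncorrected AUC and Cmax, and adds a sensitivity analysis without subjects whose T0 value exceeds 5% of Cmax. Among those retained, the bias from a lent 0 would be at most about 0.9% of cAUC under the assumed profile. The study is descriptive, and SAP 12.1.6 disclaims claims based on individual intervals. This stands too, but the corrected analysis remains the primary one.
- **All-BLOQ visits may be uncommon.** SAP 12.5.1 refers to T0 values above expectation. That points towards fewer BLOQ samples but does not say at which visit.

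A reader might infer that Day 30 usually lends to Day 1, so that Day 1 cAUC is too low and the adaptation ratio inflated. The documents do not support this. Protocol 6.2.1 requires 4 h of abstinence before the product test and at least 10 h after it, so Day 1 sampling follows at least 14 h without cigarettes. Before Day 30, up to 15 P3P a day are allowed until the evening of Day 29 (Protocol 6.2.2), and cigarette use does not lead to discontinuation (Protocol 5.2). Which visit has the lower background is not known.

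**Conclusion.** The gap is real: followed as written, SAP 7.1 can lend a slope that contains no data or is dominated by an imputed step, and no other sentence prevents it. A borrowed 0 costs 0.31 × C0 in cAUC(0-4h) relative to a 17 h half-life. That is material for the 1 mg variant or a high C0, modest for the 2 mg variant, and negligible for cCmax. The percentages rest on the assumed profile shape and on C0.

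A borrowed steep slope is the larger error, in the opposite direction. At C0 = 2 ng/mL it adds about 4.7-5.0 ng·h/mL to a 1 mg AUC of about 2.0, more than tripling it. A reader might take that as the expected harm. It should be rare, since it needs a mixed pattern at one visit and a positive slope at the other.

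How often either case arises, and whether the net effect raises or lowers the Day 30 to Day 1 ratio, cannot be determined from the documents. The point deserves correction because the rule is wrong as stated and cheap to repair, not because a large bias has been shown.

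**What to change.** In SAP 7.1, add that a visit's slope may be used, or lent to the other visit, only if all three of its pre-T0 concentrations are quantifiable. If a visit with a quantifiable C0 then has no usable slope from either visit, apply the outcome already stated for two positive slopes: baseline-corrected parameters are not calculated. Leave the rule for two positive slopes and the rule for a BLOQ C0 unchanged.

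Substituting a fixed rate from the 17 h half-life is tempting but not recommended. Applied whenever neither visit has a usable slope, it would also displace the rule in both documents for two positive slopes, a situation that about 9% of subjects (0.298²) would meet at 5% assay error. It would also replace a subject-specific method with a population constant.

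The cost is two sentences and one programming condition, in an SAP amendment before database lock as SAP 3 allows. The downside is that corrected parameters will be missing for a few more subjects; the uncorrected analysis remains available for them.
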